5.1.4. Study Drugs Administration

ALIS 590 mg or ELC will be administered QD by inhalation via nebulization over approximately 6 minutes to up to 15 minutes. Written directions for preparing and administering ALIS or ELC will be provided to subjects. On the day of study visits, ALIS or ELC administration will be the last procedure to be conducted (see Table 4).

Azithromycin 250 mg tablets dosed 1 tablet QD, and ethambutol tablets dosed at 15 mg/kg will be taken by mouth QD, with or without food. The Investigator should refer to local labeling guidance:

- To monitor AZI and ETH use
- To conduct any necessary monitoring procedures (eg, ECG monitoring, ophthalmic exams, audiology testing)

The Investigator is responsible for recording any AEs and SAEs as appropriate (see Section 9.10).

Timing of Administration

Study drugs should be administered QD around the same time each day, any time of day, in the fasted or as-fed condition.

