- c. Subjects will remain off all study drugs and should avoid initiating any new medical or non-medical therapies for MAC lung infection.
- d. Serum pregnancy testing will be performed on WOCBP at Screening. A urine pregnancy test (at least 25 mIU/mL sensitivity) must be performed for all WOCBP at all subsequent visits starting at Baseline. Women not of childbearing potential are defined as postmenopausal (ie, amenorrheic for at least 12 months), or surgically or naturally sterile.
- e. All PRO assessments will be performed prior to any other assessments (with the exception of sputum collection) and administration of study drugs and should be performed in the following order: QOL-B, PROMIS F-SF 7a, EXACT, EXACT-RS, SGRQ, FACIT-Fatigue, PGI-S-Respiratory, and PGI-S-Fatigue.
- f. Collection of data is continuous. Data will be retrieved by study staff at in-clinic visits.
- g. The physical examination will also include measurement of body weight; the measurement of height, without shoes, will only be done at Screening. All physical examinations should be performed prior to administration of study drugs.
- h. Vital signs and pulse oximetry will be assessed prior to administration of study drugs.
- i. The Baseline audiology examination must be performed during Screening or on Day 1 before administration of study drugs and evaluated by the Investigator.
- j. Tests may be performed if required by local labeling guidance; Investigators should perform all monitoring according to local label
- k. Only SAEs will be collected after the ICF is signed until Baseline.
- l. At Baseline, AEs will be assessed only after administration of study drugs. Any AE that has occurred prior to the first dose must be included in the subject's medical history, including any AEs that occur within the Screening period.

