9.3. Audiology Test

Audiology testing will be performed at study visits specified in the Schedule of Assessments (Table 4). Additional assessments may be conducted if required per local labeling guidance. Frequencies of 250, 500, 1000, 2000, 4000, and 8000 Hz will be evaluated for each ear using air conduction.

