9.5. ECG Monitoring

ECG monitoring should be performed if required by local labeling guidance to monitor QT/QTc. In the event of QT/QTc interval prolongation, monitoring should continue until QTcF returns to normal range for the subject. Investigators should manage subject per local labeling guidance.

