9.9.6. Management of Adverse Events

Initial education of adverse effect expectations is crucial for subjects initiating study drugs in order to maintain retention of subjects in the study. Based on data from the ALIS development program, there is an association with ALIS and respiratory symptoms (eg, cough, dyspnea) reported as AEs, likely from airway irritation by the inhaled antibiotic. Data observed from Study INS-212 (refractory MAC population) show that the majority of subjects treated with ALIS experienced their first AE within 60 days of initiating ALIS. Azithromycin may cause gastrointestinal symptoms. Subjects should be monitored for visual acuity when taking ethambutol.

Data have shown that specific interventions may be helpful in the management of TEAEs ([Swenson et al., 2020](#)). Pretreatment with a bronchodilator, move administration of ALIS to the evening, antitussives, post-dose gargle (warm liquid or glycerin), and other interventions may help with management of TEAEs.

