### 12.12. Audiology Tests

Audiology testing will be performed at the protocol-specified visits. Frequencies of 250, 500, 1000, 2000, 4000, and 8000 Hz will be evaluated for each ear using air conduction.

The actual, baseline, and change from baseline audiology test results will be summarized descriptively by visit, frequency, and ear.

In addition, the data will be summarized by subjects who meet CTCAE v5.0 grading criteria for hearing impairment included in [Table 8](#):

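### Protocol Table 4 gives the scheduled audiograms conflicting status, and the SAP denominator would count an untested subject as one with no hearing shift

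*Protocol*

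**What the plan says.** Protocol Table 4 (Section 6.1) schedules audiology twice, at Screening and at Month 6/EOT. The row label carries footnote j, shared with the ECG and Ophthalmic rows: "Tests may be performed if required by local labeling guidance; Investigators should perform all monitoring according to local label". The Screening cell also carries footnote i: "The Baseline audiology examination must be performed during Screening or on Day 1 before administration of study drugs and evaluated by the Investigator".

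Protocol Section 9.3 is unconditional about the scheduled tests: "Audiology testing will be performed at study visits specified in the Schedule of Assessments". It brings in the local label only afterwards: "Additional assessments may be conducted if required per local labeling guidance". Section 5.1.4, in contrast, refers the Investigator to local labeling for necessary monitoring and gives audiology as an example beside ECG and eye examinations.

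SAP Section 12.12 takes the tests as done: "Audiology testing will be performed at the protocol-specified visits". It summarizes threshold changes by visit, frequency and ear. It also grades hearing impairment by CTCAE criteria against the baseline test, using the highest post-baseline grade. Subjects who meet no grade are left out of the summary, and the denominator for percentages is the safety analysis set. The SAP's list of changes from the protocol (Table 9) does not mention audiology.

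**The concern.** One scheduled test is described both as compulsory and as dependent on the local label. Two sites could read the same protocol in good faith and act differently, and a monitor could not say consistently whether an omitted Month 6 audiogram is a deviation.

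This matters because ototoxicity is an adverse event of special interest (Protocol Section 9.9.3) and change from Baseline in audiology is a planned safety result (Section 10.7.7). If testing depends on the site, the CTC-grade table has no way to show it. A subject with no post-baseline audiogram cannot receive a grade but stays in the denominator, and so looks the same as a subject tested and found to have no shift.

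**Working it through.** **Step 1: the passages side by side.**

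| Place | Tests covered | Status given |
|---|---|---|
| Table 4, footnote j (row label) | both scheduled audiograms | conditional on local label |
| Protocol 5.1.4 | audiology generally, no visit named | conditional on local label |
| Table 4, footnote i (Screening cell) | Baseline only | compulsory, before dosing |
| Protocol 9.3, on scheduled tests | both scheduled audiograms | performed |
| Protocol 9.3 and 6.1, on local labeling | additional or unscheduled tests | left to local label |
| SAP 12.12 | protocol-specified visits | taken as performed |

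**Step 2: by visit.** For Baseline, footnote j and 5.1.4 stand against footnote i and 9.3. For Month 6/EOT, footnote i is silent, so footnote j and 5.1.4 stand against 9.3 alone. Month 6 is thus the test more plausibly omitted.

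**Step 3: is this only loose footnote wording?** The other two rows with footnote j are a check. Section 9.5 says "ECG monitoring should be performed if required by local labeling guidance to monitor QT/QTc", and Section 9.6 is conditional in the same way for eye tests. Those rows agree with the footnote. Audiology is the only footnote-j row whose own section contradicts it.

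**Step 4: effect on the SAP output.** The plan states no audiology figure to reproduce, so this is an illustration.

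- N = 50 per arm, from the planned 100 subjects (Protocol 10.1). N cancels.
- p = true proportion with a CTC-graded shift. Assumed 10%; not in the documents.
- s = share with both a baseline and a post-baseline audiogram. Assumed 100%, 80% and 50%; not in the documents.
- Testing is assumed unrelated to hearing.

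Expected number graded = N × s × p. Reported rate over the safety set = (N × s × p) / N = s × p. Rate over tested subjects = (N × s × p) / (N × s) = p.

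| s | Tested per arm | Expected graded | Over safety set | Over tested |
|---|---|---|---|---|
| 100% | 50 | 5.0 | 5.0/50 = 10% | 5.0/50 = 10% |
| 80% | 40 | 4.0 | 4.0/50 = 8% | 4.0/40 = 10% |
| 50% | 25 | 2.5 | 2.5/50 = 5% | 2.5/25 = 10% |

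If s is the same in both arms, the difference between arms becomes s × (p in the ALIS arm − p in the ELC arm), so it shrinks by the same factor.

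**The case against.** The best defence is that footnote j was meant for extra tests only. Section 9.3 words it that way, and Section 6.1 says that further monitoring recommended by the local label is done as unscheduled assessments. This narrows the ambiguity but does not remove it: the marker sits on the row label, the row holds only the two scheduled tests, and 5.1.4 points the other way.

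The defence can also say that ototoxicity is not left to audiograms. Preferred terms such as deafness, hypoacusis, tinnitus and vertigo are collected as events of special interest, and adverse events are assessed throughout. That stands; the weakness concerns audiometric results only. Randomization stratified by region should also limit imbalance between arms in who is tested, but not the dilution of rates.

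A reader might infer more than the documents support:

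- *That a site may skip both audiograms and leave no baseline.* Omitting the baseline test would breach footnote i.
- *That the eye examination has the same conflict.* Section 9.9.6 does say "Subjects should be monitored for visual acuity when taking ethambutol", but that is a general remark on adverse event management with no schedule. Section 9.6, which covers eye tests and includes visual acuity, agrees with footnote j.
- *That some sites have no ALIS label to apply.* Section 1.2 recounts approvals without claiming a complete list, no list of site countries is given, and footnote j names no drug.
- *That Exclusion 23 on hearing loss would go unchecked.* It rests on the Investigator's judgement and requires no test at any site.
- *That confidence intervals for hearing change would widen.* SAP 12.12 specifies none.

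**Conclusion.** The inconsistency is real and nothing in the SAP resolves it. It leaves the Month 6/EOT audiogram open to omission by a site that follows footnote j, and it gives the Baseline audiogram two contradictory descriptions. That some sites would omit a test is possible, not shown: the documents do not say what any local label requires.

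If tests are omitted, the CTC-grade percentages in SAP 12.12 understate hearing impairment roughly in proportion to the share tested. The 8% and 5% figures rest on an assumed true rate of 10%, on assumed shares of 80% and 50%, and on testing being unrelated to hearing. If subjects with hearing complaints were more likely to be tested, the dilution would be smaller, and a rate among tested subjects would overstate impairment; this is why the number untested must also be shown. The point is worth correcting because it concerns how a named safety risk is measured and the correction is small.

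**What to change.** 1. **Protocol.** Reconcile Table 4 footnotes i and j with Sections 5.1.4 and 9.3, so that each scheduled audiogram has one stated status at every site. Which monitoring rule applies is the sponsor's decision.
2. **SAP 12.12.** Make its text match the reconciled protocol. If an audiogram can be absent for some subjects, base the CTC-grade percentages on subjects with a baseline and at least one post-baseline audiogram, and report by arm how many were not tested.

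The cost is footnote and section wording in the protocol, plus a denominator and one extra row in a SAP table. Whether any testing is added or removed depends on the status the sponsor chooses. SAP Section 13 says no further protocol amendments are planned before unblinding. If that holds, the SAP change can still be made on its own and would remove the dilution in the reported grades, but it would leave the instructions to sites in conflict.

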6.2. Protocol Deviations

The Investigator should conduct the study in compliance with the protocol agreed to by the Sponsor and, if required, by the regulatory authority(ies), and which was given approval/favorable opinion by the IRB/EC.

The Investigator should notify the IRB/EC of any deviations from the protocol in accordance with local procedures.

6.3. Public Health Emergencies – COVID-19

During the COVID-19 public health emergency, the Sponsor, IRB/IECs, and Investigators shall follow the most current version of local guidance to assure the safety of study subjects, maintain compliance with GCP, and minimize risks to study integrity.

In anticipation that the COVID-19 pandemic may have an impact on the conduct of clinical studies, the Sponsor does not intend to screen any new subjects in this study unless the impact of the COVID-19 pandemic is deemed manageable and no longer interfering with the conduct of the study at individual sites, and subjects can safely participate in this study.

The continuity of clinical study conduct and oversight may require implementation of temporary or alternative mechanisms, which will remain in effect only for the duration of the local public health emergency. Examples of such mechanisms may include, but are not limited to, any of the following: telephone contact, virtual visits, telemedicine visits, online meetings, non-invasive remote monitoring devices, use of local clinic or laboratory locations, and home visits by skilled staff. The site should contact the Sponsor on how and when to implement temporary and/or alternative mechanism of scheduled assessments, and all decisions taken should be documented in the source documentation. Additionally, all temporary mechanisms utilized, and the resulting deviations from planned study procedures are to be documented as being related to COVID-19.

In a situation where local health authorities declare a public health emergency while the study is ongoing, the following suggested guidance should be followed:

Continuation or suspension of the study

The Sponsor, in consultation with clinical Investigators and IRBs/ECs, will determine if the protection of a subject's safety, welfare, and rights are best served by continuing or suspending the study at a specific site. Such decision will depend on specific circumstances, including the ability to conduct appropriate safety monitoring, the potential impact on the investigational product supply chain, and other considerations.

If the decision is to continue the study, the following considerations will be taken into account:

Study recruitment

The Sponsor will communicate to the sites the decision on whether to continue or suspend recruitment after considering the specific circumstances of each site, recommendation by the IRB/EC, and its local health authority mandates. If, due to COVID-19, study discontinuation exceeds the assumed rate, the Sponsor may allow enrollment past the assumed sample size (Section 10.1).

Subjects already enrolled in the study

- If a subject is not able to complete a protocol specified study visit, it may be necessary to adjust the visit schedule, convert in-clinic visits to telemedicine visits, and/or postpone study procedures until the next available in-clinic study visit. If there is information available from previous visits (ie, laboratory assessments) that requires follow-up procedures or other safety assessments, the Investigator will decide if an on-site visit or home healthcare visit is required or whether the subject's safety can be preserved by other means.
- If subjects no longer have access to the investigational product, direct-to-subjects delivery by couriers may be implemented, provided that all safety considerations and applicable health authority requirements have been addressed.
- If a subject has a documented COVID-19 infection while in the study, the event will be reported as an AE or SAE, depending on the criteria. The site will follow the guidance provided by health authorities in the treatment of those subjects.

7. PSYCHOMETRIC VALIDATION

7.1. Variables to be Validated

Psychometric validation will consist of cross-sectional and longitudinal validation analyses. At baseline, cross-sectional validation will consist of provisional modern psychometric methods.

7.1.1. Quality of Life Questionnaire – Bronchiectasis

The QOL-B is a validated, self-administered, reported outcome questionnaire used to assess symptoms, functioning, and health related quality of life in adults with non-CF bronchiectasis (Quittner et al., 2015). It measures outcomes over a recall period of 1 week. The questionnaire contains 37 items on 8 scales (physical, role, vitality, emotional, social, treatment burden, health perception, and respiratory) (Appendix 1).

The QOL-B questionnaire will be completed at study visits in the order specified in Section 6.1 and Schedule of Assessments (Table 4). Subjects will self-administer the questionnaire electronically. The QOL-B questionnaire will be the first assessment to be conducted at the specified study visits (with the exception of sputum collection, if applicable).

Each of the 37 items is scored from 1 to 4, and each of the 8 scale scores is standardized on a 0 to 100-point scale, with higher scores representing fewer symptoms or better functioning and quality of life. Scores are calculated for the 8 domains: physical, role, vitality, emotional, social, treatment burden, health perception, and respiratory.

7.1.2. PROMIS Fatigue Short Form 7a

The PROMIS F-SF 7a is a self-administered questionnaire assessing a range of self-reported symptoms over the past 7 days, from mild subjective feelings of tiredness to an overwhelming, debilitating, and sustained sense of exhaustion that likely decreases one's ability to execute daily activities and function normally in family or social roles (Ameringer et al., 2016). Fatigue is divided into the experience of fatigue (frequency, duration, and intensity) and the impact of fatigue on physical, mental, and social activities over 7 items. Examples of items are: "How often did you feel tired," and "How often were you too tired to take a bath/shower" (Appendix 2).

The PROMIS F-SF 7a will be completed at study visits in the order specified in Section 6.1 and Schedule of Assessments (Table 4). Subjects will self-administer the questionnaire electronically. The PROMIS F-SF 7a will be the second assessment to be conducted at the specified study visits.

Response options are on a 5-point Likert scale, ranging from 1=never to 5=always. The PROMIS F-SF 7a is universal rather than disease-specific and given its brevity, poses minimal burden to the subject.

7.2. Validating Variables

7.2.1. EXAcerbations of Chronic Pulmonary Disease Tool (EXACT)

The EXACT PRO was developed and qualified for use in characterizing COPD clinical endpoints (Jones et al., 2011; Leidy et al., 2010; Leidy et al., 2011; US FDA, 2013). Several of the concepts assessed by the EXACT are relevant to characterizing the symptomatic phenomena expected within bronchiectasis. These include, but are not limited to, dyspnea and fatigue. The EXACT total score measures acute, sustained, and worsening signs and symptoms exceeding subject-specific expected variability. The EXACT PRO is composed of 14 items from which a total score is generated. Domains assessed by the EXACT PRO include dyspnea, cough and sputum production, chest symptoms, difficulty expectorating, fatigue, sleep disturbance, and fear or concern (Appendix 4).

The EXACT PRO will be completed at study visits in the order specified in Section 6.1 and Schedule of Assessments (Table 4). Subjects will self-administer the questionnaire electronically.

7.2.2. Exact Respiratory Symptoms (EXACT-RS)

The E-RS is an 11-item subset of the EXACT PRO assessing exacerbations of respiratory symptoms (Leidy et al., 2014a; Leidy et al., 2014b) (Appendix 4).

The E-RS will be completed at study visits in the order specified in Section 6.1 and Schedule of Assessments (Table 4). Subjects will self-administer the questionnaire .

7.2.3. St. George's Respiratory Questionnaire (SGRQ)

The SGRQ is a self-administered instrument for the assessment of overall health, daily life, and perceived well-being among individuals with obstructive airways disease (Jones et al., 1992). The instrument consists of 50 items with 76 weighted responses grouped into a set of 17 questions. The items are divided into 2 parts and 3 categories: symptom, activity, and impact. Part 1 (symptom component) assesses an individuals' perception of their recent respiratory problems. Part 1 evaluates frequency and severity of symptoms including cough, sputum production, wheezing, breathlessness, and the duration and frequency of attacks of breathlessness and wheeze. Part 2 (activity and impact components) addresses individuals' current state. The activity component is composed of a series of items evaluating metabolic equivalence of incrementally increasingly physically demanding activities, ranging from sitting to climbing a flight of stairs. The impact component measures domains of social functioning and psychological disturbances resulting from airway disease (Appendix 5).

The SGRQ will be completed at study visits in the order specified in Section 6.1 and Schedule of Assessments (Table 4). Subjects will self-administer the questionnaire .

7.2.4. Functional Assessment of Chronic Illness Therapy (FACIT) – Fatigue Scale

The FACIT-Fatigue Scale is a short, 13-item, easy to administer, tool measuring an individual's level of fatigue during their usual daily activities during the past week (Smith et al., 2010). The level of fatigue is measured on a four-point Likert scale (4 = not at all fatigued to 0 = very much

fatigued). FACIT-Fatigue is routinely administered in studies of respiratory disease populations for accurately evaluating the common sequela of fatigue ([Appendix 6](#)).

The FACIT-Fatigue will be completed at study visits in the order specified in Section [6.1](#) and Schedule of Assessments ([Table 4](#)). Subjects will self-administer the questionnaire electronically.

7.2.5. PGI-S Respiratory

The PGI-S Respiratory score is a simple categorical rating of symptom severity. The scale is 1 = not at all to 5 = extremely severe ([Appendix 3](#)).

The PGI-S Respiratory will be completed at study visits in the order specified in Section [6.1](#) and Schedule of Assessments ([Table 4](#)). Subjects will self-administer the questionnaire electronically.

7.2.6. PGI-S Fatigue

The PGI-S Fatigue score is a simple categorical rating of symptom severity. The scale is 1 = not at all to 5 = extremely severe ([Appendix 3](#)).

The PGI-S Fatigue will be completed at study visits in the order specified in Section [6.1](#) and Schedule of Assessments ([Table 4](#)). Subjects will self-administer the questionnaire electronically.

